11.1. Adverse Events

All reported AEs will be coded according to MedDRA.

An AE is defined as treatment-emergent, if first onset or worsening is during the treatment period. Only treatment-emergent AEs (TEAEs) are accounted for in the analysis.

For each TEAE, the time relative to the start of the infusion cycle will be calculated and the TEAE will be classified as infusional AE if the onset is during the infusion cycle or within 72 hours after the end of the last infusion episode of the respective infusion cycle/visit.

All reported events will be listed and tabulated in full detail; in particular the following key figures will be presented:

- Total number of TEAEs reported by severity and overall
- Number of related TEAEs by severity and overall
- Number of TEEs and HTRs
- Number of adverse drug reactions (ADRs) and suspected ADRs
- Number of infusional AEs by severity and overall
- Number of infusion cycles with infusional AEs

Narratives will be prepared describing each death, other SAEs, and other significant AEs that are judged to be of special interest because of clinical importance, including all TEEs and HTRs reported.

The number and percentage of patients with TEAEs and the number of TEAEs will be summarized by actual treatment, unless otherwise specified, i.e. any adverse event will be considered to be associated with the most recent treatment administered, Octagam or Placebo, when summarizing the data.

Patients who are switched to the other treatment during the first study period will therefore be considered to be at risk for adverse events in both treatment groups. AE tables for the first period will summarize data within the following four groups:

1. Octagam – before or no switch
2. Octagam – after switch from Placebo
3. Placebo – before or no switch
4. Placebo – after switch from Octagam

Moreover, exposure adjusted incidence rates of TEEs will be presented under Octagam and Placebo treatment. These rates will be calculated per 100 patient months on corresponding treatment, and will be presented together with 95% confidence intervals, based on Poisson distribution. Rates will be shown under Octagam and Placebo treatment in the first period and under Octagam treatment over the total study period and for the extension period only. Also all rates will be calculated including only infusions before reduction of the infusion rate, those after reduction of the infusion rate, and including all infusions.

11.2. Clinical Laboratory Evaluations

All laboratory data will be converted to standard units during the Data Management process. The laboratory data will be listed with suitable flags indicating abnormal values (L=Lower than reference range, H=Higher than reference range).

Summary statistics for the laboratory values as well as their changes from baseline at each time will be tabulated for all laboratory parameters.

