6.1.2 Visit 2 (Week 0; Baseline of First Period)

Subjects who are eligible will visit the study site and enter the controlled phase (First Period) after randomization.

Visit 2 should take place within 3 weeks after the Screening Visit.

All eligible subjects will receive their first infusion of either 2.0 g/kg (20 mL/kg) Octagam 10% or placebo as per randomization. The following assessments will be performed:

Before infusion cycle:

- Randomization and enrollment into the double-blind treatment period.
- SF-36v2.
- Vital signs.
- Blood sample for safety laboratory (hematology and clinical chemistry).
- Blood sample for additional safety lab parameters "Panel 1" (serum haptoglobin and plasma-free hemoglobin)
- Direct Coombs' test (if positive, the antibodies responsible for the positive Coombs' test will be eluted to investigate their specificity (anti-A, anti-B or anti-D)).
- Blood sample for serum IgG.
- Blood samples for enzymes.
- CSM.
- CDASI.

Before, during and after each infusion episode:

- Administration/Infusion of IMP (2.0 g/kg [20 mL/kg] Octagam 10% or placebo given in infusion episodes over 2 to 5 consecutive days).
- Vital signs before, at least once during and at least 1 hour after each infusion episode.

At least 1 hour after the infusion cycle:

- Blood sample for additional safety lab parameters "Panel 2" (serum haptoglobin, hemoglobin, plasma-free hemoglobin, LDH).
- Direct Coombs' test (if positive, the antibodies responsible for the positive Coombs' test will be eluted to investigate their specificity (anti-A, anti-B or anti-D)).
- Wells probability score for DVT. If score is likely for DVT (≥2 points), perform Doppler scan and take blood sample for D-dimers.
- Wells probability score for PE.

In addition, AEs will be monitored and concomitant medications will be documented.

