7.3.5.2 Hemolytic Transfusion Reactions (HTRs)

HTRs can develop subsequent to IGIV therapy. IGIV-related hemolysis is associated with passive transfer of anti-A and anti-B hemagglutinins.

HTRs will be monitored as follows at pre-defined visits (see Flowchart of Study Events):

- Direct Coombs' test. If a positive result is obtained, the antibodies responsible for the positive test result will be eluted to investigate their specificity (anti-A, anti-B or anti-D).
- Additional safety lab parameters (hemoglobin, serum haptoglobin, plasma-free hemoglobin, LDH).

Intravascular hemolysis will be suspected if all of the following criteria are fulfilled (modified acc. to FDA Guidance for Industry 2008³):

- a positive direct Coombs' test result;
- a drop in hemoglobin of 2 g/dL or greater;
- a drop in serum haptoglobin to below the lower limit of normal;
- a rise in serum LDH from baseline.

In case of a patient's positive direct Coombs test the investigator has to check if the above mentioned criteria are fulfilled. The results of these additional tests and any clinical signs or symptoms potentially related to hemolysis will be documented in the patient's medical record.

Therapeutic measures managing suspected HTRs shall be initiated according to local clinical practice.

³ Guidance for Industry. Safety, Efficacy, and Pharmacokinetic Studies to Support Marketing of Immune Globulin Intravenous (Human) as Replacement Therapy for Primary Humoral Immunodeficiency. 2008

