9.2.3 Safety Analysis Plan

The safety analysis will comprise descriptive statistics, tabulations and listings of all treatment emergent adverse events (TEAEs), safety laboratory results, viral markers, vital signs, physical examination findings, and any other relevant safety information as detailed in Section 7.3.

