In case the proportion of patients with missing values is greater than 10%, or if the modified ANCOVA detailed above gives a signal of divergence, the concerned data will be further reviewed and analyzed.

The time to at least minimal, at least moderate and major improvement in TIS, and the time to confirmed deterioration in the First Period and overall, will be summarized using based on Kaplan-Meier estimates that will also be presented graphically. For the analysis of improvement variables in the first period, the time to event will be censored at the time of switch to the alternate treatment group. A stratified log-rank test will be applied for time to event variables to compare both treatment groups. Cox regression models may be applied additionally to include randomization stratum and further baseline covariates in the analysis.

To also include all data from the extension period in such Kaplan-Meier analyses, we will look at the abovementioned events and their timely relationship to the first infusion of Octagam.

To confirm the sustained benefit of treatment with Octagam 10% , response rates at Week 40 and changes from baseline to Week 40 will be presented descriptively (overall and by randomized treatment), including 95% confidence intervals.

All individual core set measures (CSMs) used for the TIS, and all other efficacy endpoints will be analyzed and presented in full detail by means of descriptive statistics, including summary and frequency tables, as well as graphs according to the general principles described in sections 8 and 12.

The development of each CSM over time will be presented graphically.

The detailed list of all tables, figures and graphs, and the analysis populations used for each analysis will be provided in a separate document later, when all feedback from authorities will be available.

11. Safety and Tolerability Analyses

The safety analysis will comprise descriptive statistics, tabulations and listings of all treatment emergent adverse events (TEAEs), safety laboratory results, viral markers, vital signs, Wells' scores, Doppler scan results, and physical examination findings.

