11.5.2. Wells Scores

To identify all occurrences of DVT and PE, Wells' probability scores will be assessed at all visits. If the DVT score is likely for DVT (≥ 2 points), a Doppler scan is performed, and D-dimers are evaluated. These parameters will be combined into a dedicated listing to facilitate the assessment of these TEAEs of special interest.

12. Reporting Conventions

The following reporting conventions will be adopted for the presentation of study data. These conventions will enhance the review process and help to standardize presentation with common notations.

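### The SAP counts reported HTRs and summarises laboratory parameters separately, so a subject who meets the protocol's four joint criteria for suspected haemolysis without a reported HTR enters no haemolysis count

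*SAP*

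**What the plan says.** HTRs are one of the two adverse events of special interest (Protocol 7.3.5). Protocol 7.3.5.2 gives a joint rule: "Intravascular hemolysis will be suspected if all of the following criteria are fulfilled". The four criteria are a positive direct Coombs' test, a haemoglobin drop of 2 g/dL or more, haptoglobin falling below the lower limit of normal, and a rise in LDH from baseline. After a positive Coombs' test "the investigator has to check if the above mentioned criteria are fulfilled", and the results are documented in the medical record. The section does not say that a subject who meets all four must be reported as an HTR.

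The laboratory data are collected. The post-cycle sample at Week 0, for example, covers "serum haptoglobin, hemoglobin, plasma-free hemoglobin, LDH" (Protocol 6.1.2), with a Coombs' test alongside.

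In the SAP:
- 11.1 tabulates reported events, gives the number of TEEs and HTRs, and plans narratives "including all TEEs and HTRs reported".
- 11.2 lists laboratory values with flags for low and high against the reference range, and states "Summary statistics for the laboratory values as well as their changes from baseline at each time will be tabulated for all laboratory parameters".
- 8.4 derives no haemolysis variable.
- 11.5.2 handles the Wells scores, Doppler scans and D-dimers differently: "These parameters will be combined into a dedicated listing to facilitate the assessment of these TEAEs of special interest".

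**The concern.** The protocol's rule is about coincidence: four findings in the same subject on the same occasion. Separate summaries by parameter cannot show coincidence. The low/high flags do not fill the gap, because two of the criteria are changes: haemoglobin can fall by 2 g/dL and stay within range, and LDH can rise from a value that was already high.

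The haemolysis result therefore depends on each site recognising the pattern and reporting it as an HTR. A site could follow 7.3.5.2 fully, record the check in the chart, report the event only as a haemoglobin decrease, and leave the subject out of every haemolysis count. About 55 sites are planned for 94 subjects, an average of 94/55 = 1.7 per site, so few sites will gain experience with the rule.

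At stake is the completeness of the reported result for a named safety outcome, when the data needed to check it will already be in the database.

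**Working it through.** The plan states no figure on this point, so there is none to reproduce. The check has three parts.

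**1. Is the joint rule applied anywhere in the SAP?**

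| Element | Protocol | SAP |
|---|---|---|
| Suspected haemolysis | Four joint criteria (7.3.5.2) | No derived variable (8.4) |
| HTR count | AE occurrence with emphasis on TEEs and HTRs (3.1.2) | From reported events (11.1) |
| Coombs' test, haptoglobin, haemoglobin, LDH | HTR monitoring (7.3.5.2) | Flagged listing and summaries by parameter (11.2); Coombs' test named in 3.2.2 |
| Combined display | – | For DVT/PE (11.5.2); none for haemolysis |

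No section combines the four criteria or counts subjects who meet them.

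**2. Can the rule be derived from the scheduled data?**

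From Protocol Table 1 and the visit descriptions in 6.1, all four components are drawn after treatment has started on six occasions: post-cycle Week 0, pre- and post-cycle Week 16, pre- and post-cycle Week 28, and Week 40 or drop-out. At the pre-cycle and final samples, haemoglobin and LDH come from the safety laboratory and haptoglobin from Panel 1. At the post-cycle samples, Panel 2 supplies all three. The Week 0 pre-infusion sample provides the reference.

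- Maximum number of assessments: 94 × 6 = 564.
- If 20% leave before Week 16 (an assumption: 19 subjects, each with a drop-out visit): 94 + 19 + 75 × 5 = 488.
- Occasions that allow a placebo comparison are post-cycle Week 0 and pre-infusion Week 16: 94 + 94 = 188 assessments, or 94 + 75 = 169 with the same loss and drop-out visits not counted.

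The other four scheduled occasions follow the start of open-label Octagam at Week 16.

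**3. What would each uncounted subject change?**

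Assumptions: 47 per arm (94/2) for the First Period, and up to 94 exposed to Octagam over the whole study if every placebo subject goes on to receive it. The documents give neither the rate of meeting the rule nor the rate of non-reporting, so 0 to 3 cases is an illustrative range, not an estimate. Intervals are Clopper-Pearson 95%. For zero cases the upper limit is 1 − 0.025^(1/n), which gives 7.5% for n = 47 and 3.8% for n = 94.

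| Cases | of 47 | of 94 |
|---|---|---|
| 0 | 0% (0 to 7.5) | 0% (0 to 3.8) |
| 1 | 2.1% (0.05 to 11.3) | 1.1% (0.03 to 5.8) |
| 2 | 4.3% (0.5 to 14.5) | 2.1% (0.3 to 7.5) |
| 3 | 6.4% (1.3 to 17.5) | 3.2% (0.7 to 9.0) |

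The 47 column applies only to the two First Period occasions.

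**The case against.** The strongest reply is that the protocol uses the four criteria as a clinical trigger and not as an endpoint. The endpoint is the occurrence of adverse events with emphasis on HTRs, and the SAP counts exactly that. A subject drops out of the count only if a site does not report what it was told to check, and several safeguards stand in the way:
- the investigator's check is mandatory after a positive Coombs' test;
- the AE definition includes abnormal laboratory findings, and marked laboratory abnormalities count as other significant AEs (Protocol 7.3.2.1), which can receive narratives under SAP 11.1;
- low haptoglobin will be flagged in the listings, and SAP 3.2.2 names the Coombs' test as a safety variable;
- monitors check the eCRF against source, the IDMC reviews safety data, and the data are medically reviewed before unblinding.

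TEE counts also come from reported events, so the contrast with SAP 11.5.2 supports a combined listing more directly than it supports a count. The list of tables is deferred, and SAP 8.4 expects further derived variables.

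Most of this stands, and it limits the point to a cheap improvement. It does not close the gap. None of the safeguards is a planned reconciliation of the four criteria with reported HTRs, and the deferred list commits to nothing. Protocol 7.3.2.2 exempts abnormalities related to the basic disease from its requirement to confirm and follow up abnormal results. LDH is one of the muscle enzymes in the TIS, so a rise could be put down to myositis.

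Two stronger readings are tempting but unsupported. A reader might infer that the stopping rule is weakened. It is not: the IDMC monitors it during the trial, while the SAP's tables are produced after the last subject completes. The rule also counts clinically significant, related, IDMC-confirmed HTRs, so laboratory suspicion should not be set against its threshold. A reader might also infer that the SAP withdraws the promise in Protocol 9.2.3 to report "and any other relevant safety information as detailed in Section 7.3". The opening of SAP 11 gives its own list, ending "vital signs, Wells' scores, Doppler scan results, and physical examination findings", but that list includes safety laboratory results, and SAP 5.1 refers to analyses identified in both documents.

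**Conclusion.** The point holds as a gap in the safety analysis that is cheap to close. As written, the SAP does not commit to applying the protocol's joint rule, and a subject who meets all four criteria without an event reported as an HTR appears only in the laboratory listings and summaries.

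The number of such subjects is unknown and may be zero. Each would add 2.1 percentage points in an arm of 47 or 1.1 points among 94 exposed, on the denominators assumed above. Meeting the rule means suspected haemolysis, not a confirmed HTR. The primary analysis is unaffected. The conclusion rests on what the SAP says; the separate list of tables, which is not available, might add a haemolysis display.

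**What to change.** In SAP 11.2:
1. Derive, per subject and occasion, whether each criterion of Protocol 7.3.5.2 and all four together are met. The occasions are post-cycle Week 0, pre- and post-cycle Weeks 16 and 28, and Week 40 or drop-out.
2. Use the Week 0 pre-infusion value as the reference for haemoglobin and LDH. At post-cycle Weeks 16 and 28, add the same-cycle pre-infusion value as a supplement, because a treatment response can lower LDH below its Week 0 level and hide a later rise.
3. State whether central or local haemoglobin and LDH are used. In some countries haematology and chemistry are done locally (Protocol 7.3.6.2), while Panel 2 is central.
4. Count subjects by actual treatment. Compare with placebo only at post-cycle Week 0 and pre-infusion Week 16 (about 47 per arm), and present Octagam alone afterwards (up to about 94 exposed).
5. Add one combined haemolysis listing that marks whether an HTR was reported, reviewed blinded before database lock.
6. Label these cases 'suspected haemolysis (laboratory)' and keep them separate from reported HTRs.

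The cost is SAP wording, one flag, one table and one listing, all from data already collected. The downside is that some cases shown will not be clinical HTRs. The label deals with this, and the placebo arm at the two comparable occasions shows the background rate.

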11.3. Viral Markers

Virology markers will be assessed at the screening visit and at the (early) termination visit; these data will be listed as well with suitable flags indicating positive results. Furthermore shift tables will be presented to show any changes in the viral status during the study.

11.4. Vital Signs

To evaluate short-term tolerance, monitoring of vital signs including blood pressure, body temperature, pulse and respiratory rate will be performed at all infusion visits. These parameters will be summarized by infusion and measurement time, using the standard set of summary statistics for both, absolute values and changes from baseline, where the baseline value is the pre-infusion measurement.

11.5. Further Safety Evaluations

11.5.1. Physical Examination

A general physical examination will be performed at the screening visit and all relevant abnormalities will be documented. The physical examination will be repeated at the termination visit (irrespective of whether termination is regular or premature), and any clinically relevant worsening from the status at screening will be documented as an AE.

11.5.2. Wells Scores

To identify all occurrences of DVT and PE, Wells' probability scores will be assessed at all visits. If the DVT score is likely for DVT (≥ 2 points), a Doppler scan is performed, and D-dimers are evaluated. These parameters will be combined into a dedicated listing to facilitate the assessment of these TEAEs of special interest.

12. Reporting Conventions

The following reporting conventions will be adopted for the presentation of study data. These conventions will enhance the review process and help to standardize presentation with common notations.

12.1. General Reporting Conventions

- All tables and data listings will be developed in landscape orientation, unless presented as part of the text in a CSR.
- Figures will in general also be presented in landscape orientation, unless presented as part of the text in a CSR. Exceptions are the Trellis plots that will be presented in portrait orientation.
- Legends will be used for all figures with more than one variable or item displayed.
- Figures will be in black and white, unless color figures have been identified as useful for discriminating presentation in the figure. Lines in figures should be wide enough to view the line after being photocopied.
- Specialized text styles, such as bolding, italics, borders, shading, superscripted and subscripted text will not be used in tables, figures and data listings unless they add significant value to the table, figure, or data listing.
- Only standard keyboard characters should be used in tables and data listings. Special characters, such as non-printable control characters, printer specific, or font specific characters, will not be used on a table, figure, or data listing. Hexadecimal character representations are allowed (e.g., μ , α , β).
- The ICH numbering convention is to be used for all tables, figures and data listings.
- All footnotes will be left justified and placed at the bottom of a page. Footnotes must be present on the page where they are first referenced. Footnotes should be used sparingly and must add value to the table, figure, or data listing. If more than four footnote lines are planned then a cover page may be used to display footnotes.
- Missing values for both numeric and character variables will be presented as blanks in a table or data listing. A zero (0) may be used if appropriate to identify when the frequency of a variable is not observed.
- All date values will be presented as DDMMYYYY (e.g., 29AUG2001) format.
- All observed time values will be presented using a 24-hour clock HH:MM format (e.g. 15:26).
- Time durations will be reported in HH:MM notation. The use of decimal notation to present (display) time durations should be avoided (e.g. 0.083h = 5min) unless it is necessary to show the computation of time differences in a table, figure, or data listing, in which case both notations may be used to display the time duration.
- All tables, figures and data listings will have the name of the program, and a date stamp on the bottom of each output.

12.2. Population Summary Conventions

- Population(s) represented on the tables or data listings will be clearly identified in the title as "Population: <name of population>" where <name of population> is any of the analysis population names or abbreviations defined in section 7 (safety analysis set (SAF), full analysis set (FAS), etc.).

- Sub-population(s) or special population(s) descriptions will provide sufficient detail to ensure comprehension of the population (e.g., ITT Females, Per-Protocol Males >60 years of age) used for analysis in a table or figure.
- Population sizes may be presented for each treatment or dosing category as totals in the column header as (N=xxx), where appropriate.
- Population sizes shown with summary statistics are the samples sizes (n) of subjects with non-missing values.
- All population summaries for continuous variables will include: N, mean, SD, median, Q1, Q3, minimum and maximum.
- All percentages are rounded and reported to a single decimal point (xx.x %).

13. Tables, Listings and Figures

To be supplied in a separate document later when all feedback from authorities will be available.
